### 14.5.5 Secondary Objective #5

The Clinical Composite Score (CCS) is a 3-level categorical variable that can take the values – Improved, Unchanged, or Worsened – at each follow-up visit. It is based on mortality, HF events, termination of device function, NYHA score, and patient global assessment. The count and proportion of subjects with each of these CCS values based on the 6-month visit will be provided.

Subjects will be included in this analysis only if they are in the Analysis Cohort and have an observed CCS.

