#### 10.6.2 CSPOT Chronic Final Device Programming

After the acute pacing protocol, the patient is implanted with a CRT-P or CRT-D device, connected to the leads that were positioned during the acute study. For CRT-D patients, the pin for RV tip and ring will be capped. After the CRT device is implanted and the pocket is closed per standard of care, the device will be programmed to the CSPOT configuration that indicated the best optimization according to ECG Belt and/or physician discretion. This includes the SAV, PAV, and VV delay. The best LVcs electrode that was used during the acute testing will also be used for chronic programming unless phrenic nerve stimulation, lead dislodgement or high capture threshold occur. If the patient is not programmed to the CSPOT configuration, the subject must be exited from the study.

The chronic device programming includes:

Feature	Programmed Value
AdaptivCRT	Nonadaptive CRT
V-V pace delay	According to best result from ECG Belt during acute study and/or physician discretion
Paced AV	According to best result from ECG Belt during acute study and/or physician discretion
Sensed AV	Programmed to a value between (Paced AV – 30ms) and (Paced AV – 100ms), according to physician discretion.
LV pacing vector	Select the best LV cathode according to ECG Belt and/or physician discretion. Select anode according to physician discretion.
Multiple Point Pacing (MPP)	Off
RV Pace Polarity	Bipolar

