### 10.7.2 Study Exit

At the completion of the 6-month follow-up visit, subjects will be exited from the study. The 6-month follow-up visit and exit visit should be combined and both a 6-month follow-up CRF and a Study Exit CRF need to be completed.

Prior to exiting a subject from the study, it is recommended to follow the subject until all ongoing AEs are resolved or unresolved with no further actions planned. Following exit, subjects will continue to receive standard medical care. Upon exiting from the study, no further study data will be collected, or study visits will occur for the subject. All data available through the time of the subject's exit will be used for analysis. Subjects who are exited from the study prior to the 6 months visit will not be replaced with another enrolled subject.

Subjects are urged to remain in the study as long as possible but may be exited from the study for any of the following situations:

• Study completion or termination

Page 41 of 88

Medtronic

- Subject lost to follow-up
- CRT-D/CRT-P device explanted and not replaced
- Implant attempt, however, no CRT-D/CRT-P was implanted

Version 4.0, 29-Apr-2022

- Subject has an invasive system modification that has intent to change the pacing behavior from the acute system configuration settings
- The following occurs during the lead positioning in the acute protocol testing:
  - Unable to place the LBBP lead
  - Unable to place the LV lead through the CS
  - Subject has a sustained sinus rate > 110 BPM
  - Subject has sustained AV block, AF, or SVT
- Subject death
- Subject did not meet inclusion/exclusion criteria
- Subject was not implanted with a Medtronic CRT-D/CRT-D device
- Subject did not provide consent or data use protection authorization
- Subject chooses to withdraw (e.g., consent withdrawal, relocation to another geographic location)
- Investigator deems withdrawal necessary (e.g., medically justified, inclusion/exclusion criteria not met, failure of subject to maintain adequate study compliance)

The following information/procedure is to be collected/performed at study exit:

- Date of Exit
- Reason for Exit
- Initial and Final Device Interrogation (with either the initial or final being an interrogate ALL) and collection of .pdd file
- Adverse Event Collection
- Device deficiencies
- Study deviations

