If discontinuation is because of safety or lack of effectiveness, the subject may be asked to be followed for collecting safety data outside the clinical investigation.

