### **10.9 System Modification**

A system modification will be reported via a System Modification CRF in the event the initially implanted device or leads require non-invasive modification (repositioning of leads, device battery change out) and the intent is to continue the same pacing behavior as the original system was configured.

If the implanted device or leads require an invasive modification (e.g., device or lead explant, device or lead replacement/repositioning with intent to change pacing behavior from original system) the System Modification CRF will be completed and the subject will be exited after all system and/or procedure related AEs have been resolved or remain unresolved with no further action planned.

In the event of a non-invasive system modification, the follow-up schedule for the subject will remain unchanged.

Form

Version 4.0, 29-Apr-2022 Page 43 of 88

For any system modification the following activities are required:

- Complete the System Modification CRF regarding details of the system modification procedure
- Device interrogation on the system modification if at all possible:
  - if device is explanted: Interrogate ALL and collect .pdd file
  - if new device implanted: Interrogate ALL and collect .pdd file
  - if lead revision: Interrogate (with either initial or final being an interrogate ALL) and collect .pdd file
- Adverse Event Collection if applicable
- Device Deficiencies if applicable
- Study Deviations if applicable

All explanted product should be returned to Medtronic for analysis when permissible by local laws and regulations.

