### 14.5.4 Secondary Objective #4

For each subject with LVESV measured at implant and 6-month visit, LVESV change will be calculated as a relative change from baseline:

(LVESV measured at 6 months) – (LVESV measured at baseline) LVESVI measured at baseline

[figure not shown]
LVESV change will then be summarized with mean, 95% confidence interval, median,  $25^{th}$  and  $75^{th}$  percentile, and minimum and maximum.

Subjects will be included in this analysis only if they are in the Analysis Cohort and successfully complete CRT implant and the 6-month follow-up visit.

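### Early exits without a death, heart-failure event or device termination get no Clinical Composite Score and leave the denominator, which can raise the reported proportion Improved

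*Protocol*

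**What the plan says.** Protocol 14.5.5 defines a three-level score (Improved, Unchanged, Worsened): "It is based on mortality, HF events, termination of device function, NYHA score, and patient global assessment". The output is descriptive: "The count and proportion of subjects with each of these CCS values based on the 6-month visit will be provided". The inclusion rule is "Subjects will be included in this analysis only if they are in the Analysis Cohort and have an observed CCS". The readable text does not say when a score counts as observed.

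The two preceding objectives (14.5.3 and 14.5.4, LVEF and LVESV) use a different rule. They require that subjects "successfully complete CRT implant and the 6-month follow-up visit". The CCS rule has no such condition.

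On exits, Protocol 10.7.2 lists reasons for which a subject may be exited, among them: "Subject has an invasive system modification that has intent to change the pacing behavior from the acute system configuration settings". Section 10.9 is firmer about invasive modification: "the subject will be exited after all system and/or procedure related AEs have been resolved or remain unresolved with no further action planned". Section 10.6.2 adds a mandatory exit: "If the patient is not programmed to the CSPOT configuration, the subject must be exited from the study".

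The data required at exit (10.7.2) are date, reason, device interrogation, adverse events, device deficiencies and deviations. NYHA and patient global assessment are not listed. By Table 6 and 10.7.1, the global assessment is scheduled only at 6 months; NYHA is taken at baseline and at 6 months. Section 10.7.2 also says that data up to exit are used, that none are collected afterwards, and that exited subjects are not replaced. Protocol 14.1 and SAP 7.4 plan no imputation of outcomes and summarize missingness as a binary variable.

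**The concern.** After implant there is no comparison group. Protocol section 6 says the 6-month clinical endpoints are there to assess the chronic efficacy of CSPOT, so the proportion Improved will be read at face value.

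One route to a missing score is an operation intended to move the subject off the tested pacing. Where that operation follows a poor response, the chance of being scored depends on the outcome being scored. The proportion then describes those who stayed on CSPOT long enough to attend the visit. The loss is permanent, because NYHA and the global assessment cannot be reconstructed at analysis if they were not recorded before exit.

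**Working it through.** **Step 1. Who gets a score under the readable text**

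- *Death, HF event or termination of device function before 6 months.* Each is a CCS component, known without a visit, and pre-exit data are kept. These subjects can be scored Worsened, although 14.5.5 does not say so outright.
- *Device explanted and not replaced.* Plausibly termination of device function, so scorable in the same way.
- *Invasive modification intended to change pacing, device working, no HF event.* Exited, with no post-implant NYHA and no global assessment. No score.
- *Withdrawal or loss to follow-up without one of the three events.* No score.
- *Not programmed to CSPOT after implant.* Exited under 10.6.2. Can be in the Analysis Cohort, but never received chronic CSPOT pacing, so a missing score says nothing about response to it.
- *Failed LBBP or LV lead placement.* Outside the Analysis Cohort, so not affected.

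The gap is the third and fourth groups.

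**Step 2. Inputs for size**

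From the documents: up to 60 subjects (Protocol 14), with sample size set by sites, enrollment rate and timing (14.8). No expected CCS proportion, dropout rate or re-operation rate is given, so there is no plan figure to reproduce.

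Assumed here: all 60 are in the Analysis Cohort, implanted and programmed to CSPOT; 3, 6, 9 or 12 exit early (5% to 20%); 50%, 60% or 70% of completers are Improved; and none, half or all of the early exits are already scored Worsened through an event component.

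**Step 3. Formulas**

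Let N = 60, C = completers, I = completers Improved, k = early exits scored Worsened through an event, and u = N − C − k = unscored exits.

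- Reported under 14.5.5: I / (C + k)
- Unscored exits counted as not Improved: I / N
- All unscored exits Improved: (I + u) / N

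**Step 4. Illustration: 6 exits, C = 54, I = 32**

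- No exit scorable (k = 0): 32/54 = 59.3% (exact 95% CI 45.0 to 72.4).
- All exits not Improved: 32/60 = 53.3% (40.0 to 66.3). The reported figure is 5.9 points higher.
- Half the exits already Worsened (k = 3): 32/57 = 56.1%, which is 2.8 points higher than 53.3%.
- All exits already Worsened (k = 6): 32/60 = 53.3%, no difference.
- All six exits in truth Improved: 38/60 = 63.3%. The reported 59.3% would be about 4 points too low.

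The sign changes between three and four. If 3 of the 6 unscored exits were in truth Improved, the full figure is 35/60 = 58.3%, below the reported 59.3%; if 4 were, it is 36/60 = 60.0%, above it.

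**Step 5. Range**

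Taking unscored exits as not Improved, the difference over the grid runs from 0 (every exit already scored) to 14.2 points (12 exits, none scored, 34 of 48 completers Improved: 34/48 = 70.8% against 34/60 = 56.7%). With 3 exits, none scored, and 28 of 57 Improved, it is 2.5 points (49.1% against 46.7%).

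**The case against.** A reader might infer that every treatment failure drops out, so that the proportion Improved is necessarily inflated. The documents do not support that, for four reasons.

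1. The CCS rule omits the completed-visit condition used for LVEF and LVESV, and mortality is a component although a dead subject cannot attend. The natural reading is that the event components score without a visit. Much clinical failure is therefore already captured. This stands, and it narrows the point to exits without an event.
2. Lack of effectiveness is not among the exit reasons in 10.7.2. The phrase "If discontinuation is because of safety or lack of effectiveness" only introduces possible safety follow-up outside the investigation, and 10.7.5 discourages investigator withdrawal without compelling medical justification. This stands.
3. Exits also arise from relocation, consent withdrawal, loss to follow-up or lead problems unrelated to response. Direction is therefore not established. This stands too, although an operation to move off CSPOT pacing more plausibly goes with a poor response than a good one.
4. SAP 7.9, where the objectives are evaluated, is largely blacked out and may contain a scoring rule, so the SAP cannot be said to lack one. However, the inclusion rule in Protocol 14.5.5 is readable, and no SAP wording can supply assessments that were never collected at exit.

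SAP 7.1.1 also tabulates exits by reason, partly to judge their effect on results. That helps a careful reader but does not link unscored subjects to the CCS table.

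**Conclusion.** The point holds in a limited form. Subjects who leave CSPOT pacing or withdraw early, without a death, HF event or termination of device function, have no CCS under the readable plan and leave the denominator. The proportion Improved can be too high as a result. It is unaffected if every failure is already scored through an event, and too low if enough unscored exits were in truth Improved.

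The documents do not fix the size. On the assumed inputs the overstatement is 0 to 14.2 points when unscored exits are counted as not Improved, and 5.9 points in the illustration with 6 of 60. That is smaller than the sampling uncertainty at this sample size: the exact interval around 32/54 spans 27.4 points (72.4 − 45.0). No hypothesis test is affected. This is a descriptive secondary objective in an exploratory feasibility study, so priority is modest. The collection part should be settled first, because it cannot be repaired afterwards.

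**What to change.** 1. In Protocol 10.7.2, add NYHA class and patient global assessment to the data collected at early exit where a visit is possible, and use them for the CCS.
2. In 14.5.5, define when a score counts as observed. State that a death, an HF event or termination of device function before 6 months is scored Worsened whether or not the visit takes place. Align the SAP if its blacked-out text does not already say this.
3. Report the CCS with all Analysis Cohort subjects implanted and programmed to CSPOT as denominator, and a separate missing row broken down by exit reason.
4. Add a sensitivity analysis that counts unscored exits as not Improved.

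Pacing-changing modifications should not all be scored Worsened automatically in the main summary. That would add a component which 14.5.5 does not contain and would mislabel subjects who were clinically better.

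The cost is two form items, a few lines of Protocol and SAP text and one extra table row, with a proportion Improved that may come out slightly less favourable.

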# 14.8 Sample Size Determination

# CSPOT (Conduction System Pacing Optimized Therapy) Clinical Investigation Plan Version 4.0, 29-Apr-2022 Page 68 of 88 Medtronic

Because this is an exploratory feasibility study, sample size has been determined by the number of possible sites, enrollment rates and timing for completion.

### 15. Ethics

# 15.1 Statement(s) of Compliance

This study will be conducted in compliance with international ethical and scientific quality standards, known as GCP. GCP includes review and approval by an independent EC before initiating a study, continuing review of an ongoing study by an EC, and obtaining and documenting the freely given informed consent of a subject before initiating the study.

The CSPOT study was designed to reflect the GCP principles outlined in ISO 14155:2020 and other international clinical requirements outlined below. These include the protection of the rights, safety and well-being of human subjects, controls to ensure the scientific conduct and credibility of the clinical investigation and the definition of responsibilities of the sponsor and investigators. In accordance with ISO 14155:2020, the sponsor shall avoid improper influence on, or inducement of, the subject, monitor, any investigator(s) or other parties participating in, or contributing to, the clinical investigator(s) or other parties participating in or contributing to the subject, sponsor, monitor, other investigator(s) or other parties participating in or contributing to the clinical investigation. AE and DD handling in the CSPOT study is ISO 14155:2020 compliant for all participating geographies.

The principles of the DoH have been implemented through the IC process, EC approval, study training, clinical trial registration, pre-clinical testing, risk-benefit assessment and publication policy.

Ultimately, all study sites in all geographies will follow and comply with:

- Principles of DoH
- 21 CFR Part 11 (Electronic Records, Electronic Signatures)
- 21 CFR Part 54 (Financial Disclosure by Clinical Investigators)
- The CTA
- The procedures described within this CIP
- Local EC Requirements

# CSPOT (Conduction System Pacing Optimized Therapy) Clinical Investigation Plan Version 4.0, 29-Apr-2022 Page 69 of 88 Medtronic

In addition to the regulatory requirements outlined above, the study will be conducted according to federal, national and local laws, regulations, standards, and requirements of the countries/geographies where the study is being conducted. These include but are not limited to:

- In the United States, the study will be conducted under an FDA IDE in compliance with 21 CFR Parts:
  - 50: Protection of Human Subjects
  - 54: Financial Disclosure by Clinical Investigators
  - 56: IRBs
  - 812: IDEs
- In Europe the study will be conducted in compliance with the local regulations

The study will be publicly registered prior to in accordance with the 2007 FDAAA and DoH on http://clinicaltrials.gov (PL 110-85, section 810(a)). In addition, the study may be registered in local regulatory databases where required by local law.

Approval of the CIP and CIP amendments is required from the following groups prior to any study procedures at a study site:

- Medtronic
- Principal Investigators (where required by local law/regulations)
- Geography-specific regulatory authorities (if regulatory approval is required)
- An independent medical EC or IRB.

Similarly, approval of subsequent revisions to the CIP is required at each study site from the abovementioned groups prior to implementation of the revised CIP at the study site.

# 16. Study Administration

### 16.1 Monitoring

It is the responsibility of Medtronic to ensure proper monitoring of this study. Trained Medtronic personnel or delegates appointed by Medtronic may perform study monitoring at the study site in order to ensure that the study is conducted in accordance with the CIP, the CTA, and the applicable regulatory and local requirements. Medtronic, or delegates, must therefore be allowed direct access to the subjects' case histories (clinic and hospital records, and other source data/documentation) upon request as per the IC, Research Authorization (where applicable) and CTA. The principal investigator should also be available during monitoring visits.

### 16.1.1 Monitoring Visits

Frequency of monitoring visits may be based upon subject enrollment, study compliance, number of adverse events, number of deviations, observations from previous monitoring visits and any suspected inconsistency in data that requires investigation. Regulatory documents may be reviewed at each

CSPOT (Conduction System Pacing Optimized Therapy) Clinical Investigation Plan	Form
merupy) ennear investigation i fan	
Version 4.0, 29-Apr-2022 Page 70 of 88	Medtronic

study site. Monitoring for the study, including, site initiation visits, interim monitoring visits, and closeout visits will be done in accordance to the study-specific monitoring plan.

Monitoring visits may be conducted periodically to assess study site progress, the investigator's adherence to the CIP, regulatory compliance including but not limited to EC approval and review of the study, maintenance of records and reports, and review of source documents against subject CRFs in accordance to the study-specific monitoring plan. Monitors review study site regulatory and study compliance by identifying observations of non-compliance and communicating those observations along with recommendations for preventative/corrective actions to study site personnel. Monitors may work with study personnel to determine appropriate corrective action recommendations and to identify trends within the study or at a particular study site.

The Investigator will permit study related monitoring, audits, IRB review and regulatory inspections by providing direct access to source data and source documents.

Medtronic will request that the study site upload identified subject case history files and regulatory documents to a secure, password-protected website prior to remote monitoring visits.

### 16.2 Data Management

Data will be collected using an electronic data management system for studies. eCRF data will be stored in a secure, password-protected database which will be backed up nightly. Data will be reviewed using programmed and manual data checks. Data queries will be made available to study sites for resolution. Study management reports may be generated to monitor data quality and study progress. At the end of the study, the data will be frozen and will be retained indefinitely by Medtronic.

All records and other information about subjects participating in this study will be treated as confidential. Data will be transferred and processed by Medtronic or a third party designated by Medtronic in a key coded form. If it's impossible to pseudonymize (where the subject's name cannot be removed, such as fluoroscopy images) from the data carrier, data will not be transferred electronically.

Procedures in the CIP require source documentation. Source documentation will be maintained at the study site. Source documents, which may include worksheets, subject medical records, programmer printouts, and interrogation files, must be created and maintained by the investigational study site team.

The investigator will clearly mark clinical records to indicate that the subject is enrolled in this clinical investigation.

The data reported on the CRFs shall be derived from source documents and be consistent with these source documents, and any discrepancies shall be explained in writing. See Section 16.3 for CRFs and data collection elements that may be considered source.

Device data from transmissions and any save-to-disk data collected at office visits will be sent to Medtronic. Upon receipt, device data will be maintained with databases and retrieved for analysis and reporting.

Investigator will be required to sign off on all entered and completed data on the eCRF.

Version 4.0, 29-Apr-2022

Page 71 of 88

